4.5.2 Management Algorithms for Immuno-oncology Agents

I-O agents are associated with AEs that can differ in severity and duration from AEs caused by other therapeutic classes. Nivolumab, ipilimumab, and BMS-986205 are considered I-O agents in this protocol. Early recognition and management of AEs associated with I-O agents

may mitigate severe toxicity. Management algorithms have been developed from extensive experience with nivolumab and ipilimumab to assist investigators in assessing and managing the following groups of AEs:

- Gastrointestinal
- Renal
- Pulmonary
- Hepatic
- Endocrinopathies
- Skin
- Neurological

The clinical nature of AEs noted with BMS-986205 will determine the role of the above algorithms for use in toxicities related to its use in this study.

The algorithms recommended for utilization in this protocol are included in [Appendix 5](#).

4.5.3 Guidelines for Dose Modification

Subjects will be monitored continuously for AEs while on study drug. Subjects will be instructed to notify their physician immediately for any and all AEs. The criteria presented in this section and [Table 4.5.3-1](#) for dose modifications for BMS-986205 are meant as general guidelines.

Dose modification may occur in the setting of lower grade AE and/or be more conservative than indicated in Table 4.5.3-1 based on the clinical judgment of the investigator and in consultation with the Sponsor/Medical Monitor.

- Dose reductions of BMS-986205 should be to the previous lower dose level; subjects receiving 25 mg of BMS-986205 will not undergo any (further) dose reductions.
- If several AEs of varying grade or severity occur simultaneously, the dose modification applied should be the greatest reduction applicable.
- Assessment of causality (ie, chronology, confounding factors such as disease, concomitant medications, diagnostic tests, and previous experience with the agent) must be determined and documented by the investigator prior to dose modification.
- If the same AE recurs despite a dose reduction, a second dose reduction versus discontinuation of BMS-986205 will be discussed and agreed upon by the Sponsor/Medical Monitor and investigators, if criteria for discontinuation are otherwise not met.
- No more than 2 dose reductions of BMS-986205 will be allowed per subject. Dose escalation after a dose reduction may occur in limited circumstances (such as a change in attribution of an AE) after discussion and agreement of the Sponsor/Medical Monitor and investigators.
- Skipped doses will not be administered within the same cycle.
- For an AEs leading to dose modification, BMS-986205, nivolumab, and ipilimumab (where applicable) should be interrupted to allow recovery from the AE; see [Section 4.5.4](#) for delay criteria. Re-initiation of study drug cannot occur until AE decreases to \leq Grade 1 or baseline assessment. See [Section 4.5.5](#) for resumption after dose delays.
- During the DLT evaluation period, if the dose is reduced and a subject experiences a DLT at the lower dose, this DLT will be attributed to the highest dose level administered.

- For data collection and analysis purposes, all subjects will continue to be classified by the original treatment arm.

Table 4.5.3-1: Dose Modifications

Dose Modification Criteria for Drug-related Adverse Events	BMS-986205 Monotherapy Modification at the Next Dose (Part 1 Only)	BMS-986205 Combination Modification at the Next Dose (Parts 1, 2 and 3)
Methemoglobin ≥ 15%	Decrease 1 level of BMS-986205	Interrupt dosing until improvement and decrease 1 level of BMS-986205 in combination with same dose of nivolumab or nivolumab and ipilimumab.
Methemoglobinemia with Grade 3 AEs such as hypoxia and hemolysis	Interrupt BMS-986205. Continuation of BMS-986205 after recovery at a lower dose level may be considered after discussion with the Study Director/Medical Monitor. Subjects may proceed to get nivolumab monotherapy.	Interrupt BMS-986205. Continuation of BMS-986205 after recovery at a lower dose level may be considered after discussion with the Study Director/Medical Monitor. Subjects may proceed to get nivolumab monotherapy or nivolumab and ipilimumab.
Methemoglobinemia with Grade 4 AEs such as hypoxia and hemolysis	Permanent discontinuation of BMS-986205. Subjects may proceed to get nivolumab monotherapy.	Permanent discontinuation of BMS-986205. However, treatment with nivolumab or nivolumab and ipilimumab may continue after discussion between PI and Medical Monitor.
QTcF > 500 msec confirmed by at least 1 repeat ECG and at least 60 msec above baseline	Interrupt if needed to optimize electrolyte management. If persists after electrolyte optimization (including dose modification of BMS-986205, if necessary), discontinue. Subjects may proceed to get nivolumab monotherapy.	Interrupt if needed to optimize electrolyte management. If persists after electrolyte optimization (including dose modification of BMS-986205, if necessary), discontinue. However, treatment with nivolumab or nivolumab and ipilimumab may continue after discussion between PI and Medical Monitor.
Any other drug-related ≥ Grade 3 adverse event that does not meet permanent discontinuation criteria (Section 4.5.6)	Decrease 1 level of BMS-986205	Decrease 1 level of BMS-986205 in combination with same dose of nivolumab or nivolumab and ipilimumab.
Grade 2 LFT abnormalities that do not resolve within 1 week	Interrupt BMS-986205. Continuation of BMS-986205 after recovery at a lower dose level may be considered after discussion with the Study Director/Medical Monitor. Subjects may proceed to get nivolumab monotherapy.	NA
Grade 2 LFT abnormalities	Interrupt dosing until improvement to	NA

Table 4.5.3-1: Dose Modifications

Dose Modification Criteria for Drug-related Adverse Events	BMS-986205 Monotherapy Modification at the Next Dose (Part 1 Only)	BMS-986205 Combination Modification at the Next Dose (Parts 1, 2 and 3)
that resolve in 1 week	Grade 1 or baseline and resume at same dose. If recurrence of Grade 2 LFT elevations, decrease 1 level.	

Abbreviations: AE = adverse event; ECG = electrocardiogram; LFT = liver function test; QTcF = QT interval corrected for heart rate using Fridericia's formula; NA = not applicable; PI = principal investigator.

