4.5.6 Guidelines for Permanent Discontinuation

Subjects will be required to permanently discontinue all study drugs for the following AEs:

- Clinical deterioration, as assessed by the investigator
- Any occurrence of serotonin syndrome
- Any Grade 3 non-skin, drug-related AE lasting > 7 days, or recurs with the following exceptions for laboratory abnormalities, neurologic toxicity, drug-related uveitis, pneumonitis, bronchospasm, hypersensitivity reactions, infusion reactions, endocrinopathies (and diarrhea and colitis for subjects receiving ipilimumab):
 - Grade 3 drug-related neurologic toxicity, uveitis, pneumonitis, bronchospasm, myocarditis, hypersensitivity reaction, or infusion reaction of any duration requires discontinuation; for subjects receiving ipilimumab, Grade 3 diarrhea and colitis of any duration also require discontinuation
 - Grade 3 drug-related endocrinopathies, adequately controlled with only physiologic hormone replacement do not require discontinuation. Adrenal insufficiency requires discontinuation regardless of control with hormone replacement.
 - Grade 3 drug-related laboratory abnormalities do not require treatment discontinuation except:
 - ◆ Grade 3 drug-related thrombocytopenia > 7 days or associated with bleeding requires discontinuation
 - ◆ Any drug-related liver function test (LFT) abnormality that meets the following criteria require discontinuation:
 - Grade ≥ 3 drug-related AST, ALT or Total Bilirubin requires discontinuation*
 - Concurrent AST or ALT $> 3 \times$ ULN and total bilirubin $> 2 \times$ ULN

* In most cases of Grade 3 AST or ALT elevation, study treatment will be permanently discontinued. If the investigator determines a possible favorable benefit/risk ratio that warrants continuation of study treatment, a discussion between the investigator and the BMS Medical Monitor/designee must occur.

- Any Grade 4 drug-related adverse event or laboratory abnormality (including but not limited to creatinine, AST, ALT, or Total Bilirubin), except for the following events which do not require discontinuation:
 - Grade 4 neutropenia ≤ 7 days
 - Grade 4 lymphopenia or leukopenia or asymptomatic amylase or lipase

- Isolated Grade 4 electrolyte imbalances/abnormalities that are not associated with clinical sequelae and are corrected with supplementation/appropriate management within 72 hours of their onset

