- Grade 4 drug-related endocrinopathy adverse events, such as, hyper- or hypothyroidism, or glucose intolerance, which resolve or are adequately controlled with physiologic hormone replacement (corticosteroids, thyroid hormones) or glucose-controlling agents, respectively, may not require discontinuation after discussion with and approval from the BMS Medical Monitor.
- Any dosing delay lasting > 6 weeks will be cause for permanent discontinuation. Extensions to the period of dose delays may be granted for individual subjects on a case-by-case basis after specific consultation and agreement between the investigator and BMS Medical Monitor in settings where benefit/risk may justify continued study drug (eg, subject deriving clinical benefit who requires prolonged steroid taper for management of non-DLT immune-related AEs or experiences delays for management of a non-drug-related AE).
- Accordingly, dosing delays to allow for prolonged steroid tapers to manage drug-related AEs are allowed. Additionally, dosing delays > 6 weeks that occur for non-drug-related reasons may be allowed if approved by the BMS Medical Monitor.
- Prior to re-initiating treatment in a subject with a dosing delay lasting > 6 weeks, the BMS Medical Monitor must be consulted.
- Tumor assessments should continue as per protocol even if dosing is delayed.

All subjects who discontinue investigational product should comply with protocol-specified follow-up procedures as outlined in [Section 3.1.2](#). The only exception to this requirement is when a subject withdraws consent for all study procedures including post-treatment study follow-up or loses the ability to consent freely (eg, is imprisoned or involuntarily incarcerated for the treatment of either a psychiatric or physical illness).

If study drug is discontinued prior to the subject's completion of the study, the reason for the discontinuation must be documented in the subject's medical records and entered on the appropriate CRF page

4.5.7 *Detection and Management of Methemoglobinemia*

BMS-986205 may produce a p-chloroaniline metabolite. P-chloroaniline has been associated with the production of methemoglobin. Symptoms of methemoglobinemia are related to the lack of oxygen delivery to tissues and are proportional to the fraction of methemoglobin, as described below for subjects with normal hemoglobin levels.

Symptoms associated with elevations of methemoglobin are as follows:

- 0% to 10% - Usually asymptomatic

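### After methemoglobinemia with a Grade 4 event, Table 4.5.3-1 allows the antibodies to be given, but Section 4.5.6 requires every study drug to stop

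*Combined protocol and SAP*

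**What the plan says.** The first column of Table 4.5.3-1 is headed "Dose Modification Criteria for Drug-related Adverse Events". One row covers methemoglobinemia accompanied by Grade 4 events, with hypoxia and hemolysis as examples.

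- Combination column (Parts 1, 2 and 3): "Permanent discontinuation of BMS-986205. However, treatment with nivolumab or nivolumab and ipilimumab may continue after discussion between PI and Medical Monitor".
- Monotherapy column (Part 1 only): "Permanent discontinuation of BMS-986205. Subjects may proceed to get nivolumab monotherapy". No consultation is mentioned.

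Section 4.5.6 opens with "Subjects will be required to permanently discontinue all study drugs for the following AEs". Its list includes "Any Grade 4 drug-related adverse event or laboratory abnormality", "except for the following events which do not require discontinuation". Four exceptions follow:

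- neutropenia of 7 days or less
- lymphopenia, leukopenia, or asymptomatic amylase or lipase elevation
- isolated, corrected electrolyte abnormalities
- controlled endocrinopathy

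Only the last gives the Medical Monitor a role: such events "may not require discontinuation after discussion with and approval from the BMS Medical Monitor".

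Under Sections 4 and 4.1, study drug means BMS-986205, nivolumab and ipilimumab.

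**The concern.** The two rules give different instructions for the same event. The table permanently stops one drug and allows the others; Section 4.5.6 permanently stops all of them. An investigator who follows the table, including the required discussion with the Medical Monitor, still breaches a mandatory stopping rule after a life-threatening event, and the case would count as a protocol deviation.

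There is also a gap on attribution. For methemoglobin elevation with a Grade 3 event, Section 4.5.4 delays the antibodies too if their contribution cannot be excluded, and gives dyspnea with possible pneumonitis as its example. The Grade 4 row carries no such condition.

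**Working it through.** The plan gives no figure to reproduce, so the check compares the texts and then sizes the problem.

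**1. Do both rules cover the same event?** Yes. Both are limited to drug-related events. Because study drug includes all three products, an event caused by BMS-986205 alone is still drug-related under Section 4.5.6.

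**2. Does an exception apply?** No. None of the four covers methemoglobinemia, hypoxia or hemolysis.

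**3. Does other text settle the conflict?**

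| Place | What it does | Resolves the conflict? |
|---|---|---|
| Section 3.5 | Makes the Section 4.5.6 reasons mandatory grounds for discontinuation | No; supports 4.5.6 |
| Section 4.5.1 | Cites 4.5.3 and 4.5.6 together | No; gives no precedence |
| Section 4.5.3, introduction | Describes the table as general guidelines | No; weakens the table |
| Table 4.5.3-1, row for any other Grade 3 or higher event | Yields to 4.5.6 | No; applies to that row only |
| Section 4.5.4, opening | Names 4.5.6 as the list for stopping all drugs | No; supports 4.5.6 |
| Section 4.5.4, later text | Allows antibodies while BMS-986205 is delayed for methemoglobin | No; covers delays, and its associated-event criterion is Grade 3 |
| Section 4.5.5 | Makes a permanent stop yield to 4.5.3 | No; covers delays over 6 weeks only |
| Section 4.5.6, footnote | Allows case-by-case continuation | No; Grade 3 AST or ALT only |

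**4. Which way does the conflict run?** One way only. The table permits antibodies but does not require them, so stopping everything complies with both sections. BMS-986205 stops permanently under either rule.

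**5. How often might it arise?** Either rule would have required BMS-986205 to be discontinued, so discontinuations for methemoglobinemia bound the number of these events.

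- Discontinuations for methemoglobinemia by 15-Nov-2017: 0 (Section 1.5.1).
- Combination subjects in this study by that date: 397 (Section 1.5.2).
- One-sided 95% upper bound: 1 − 0.05^(1/397) = 0.0075, or 0.75%.
- Two-sided 95% upper limit: 1 − 0.025^(1/397) = 0.0092, or 0.92%.
- Planned Part 3 expansion (Section 3.1.7): 5 × 40 + 40 = 240, the last 40 being the maximum for the mixed cohort.
- Events at the one-sided bound: 240 × 0.00752 = 1.80. At the two-sided limit: 240 × 0.00925 = 2.22. The point estimate is 0.
- Adding three safety cohorts of up to 12 DLT-evaluable subjects at the expansion dose: 240 + 36 = 276, and 276 × 0.00752 = 2.08.

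**The case against.** The strongest reply is that the sponsor's intent can be inferred. For methemoglobin and QTcF toxicity, Section 4.5.4 delays BMS-986205 alone and lets the antibodies continue, so these look like deliberately drug-specific rules. The catch-all row's reference to other events suggests that the named rows are specific carve-outs. The combination cell also requires discussion with the Medical Monitor, so the sponsor is consulted before antibodies continue. On this view the protocol lacks only a cross-reference, and calling the site's action a breach assumes that Section 4.5.6 prevails.

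The inference about intent is reasonable, but no text states it. The Section 4.5.4 permission stops at dose delays, and where Section 4.5.6 wants Medical Monitor discretion for a Grade 4 event, it says so. The table is offered as guidance; Section 4.5.6 is worded as a requirement.

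Other points stand as limits on the concern:

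- Section 4.5.3 says all drugs should be interrupted for events leading to dose modification, bars restart before recovery to Grade 1 or baseline, and requires documented causality. This limits clinical risk, but it governs when dosing may restart, not whether it may. The interruption is worded as should, and the delay criteria it points to in Section 4.5.4 hold only BMS-986205 for methemoglobin events.
- The monotherapy cell probably has little remaining use. Section 1.5.2 reports the MTD with nivolumab as established, so escalation appears finished.
- The frequency bound counts any discontinuation for methemoglobinemia, which is broader than the Grade 4 subset. It also leaves out remaining Part 2 subjects.
- The Grade 3 methemoglobinemia row has a similar tension with the Section 4.5.6 rule on Grade 3 non-skin events lasting over 7 days. That is a further reason to tidy the text and does not weaken the Grade 4 point.

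**Conclusion.** The concern holds. For this event the protocol contains a contradictory stopping rule. Rarity and the one-sided direction keep it below the most serious class, but it should be corrected.

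The estimate of 0 to about 1.8 Part 3 expansion events assumes that the doublet bound applies to the triplet. The true number is probably near zero. Peak methemoglobin was 16%, at 200 mg and without clinical sequelae; no other subject exceeded 10%, and no clinically significant event occurred at 100 mg. Part 3 is capped at 100 mg (Section 3.1.1.2), and by 3-May-2018 dosing had already fallen to 50 mg in melanoma, with 25 mg opened in NSCLC (Section 1.4.4.4). The contradiction itself rests on the text and does not depend on these figures.

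**What to change.** Add a separate sentence to Section 4.5.6, outside the list of events that need no discontinuation, because BMS-986205 does stop here. Suggested wording:

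> Exception: for Grade 4 AEs attributable to methemoglobinemia and not to nivolumab or ipilimumab, BMS-986205 is permanently discontinued; nivolumab (and ipilimumab in Part 3) may be given after recovery per Section 4.5.3 and after discussion with the Medical Monitor.

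Put the same condition in both cells of the Grade 4 methemoglobinemia row, so that the monotherapy cell also requires the discussion. This also closes the attribution gap.

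If the sponsor intends all drugs to stop, delete the antibody permission from both cells instead. That clinical choice is the sponsor's.

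The cost is one sentence and two cell edits (or two deletions) at the next amendment, with no new procedures or data.

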4.5.4 Dose Delays due to Toxicity

- Subjects who experience a DLT must have study drug held. Subjects who are required to permanently discontinue all study drugs are listed in [Section 4.5.6](#). In addition, all Grade 2 hepatic, pulmonary, renal, gastrointestinal, and neurological AEs should be evaluated and managed per the toxicity management algorithms ([Appendix 5](#)). Subjects not meeting guidelines for permanent discontinuation will be permitted to resume therapy based on the criteria specified below in [Section 4.5.5](#). Subjects eligible to resume study drug will resume study drug at the treatment visit following their last received study drug dose.
- The scheduled tumor assessments (ie, CT/MRI, positron emission tomography [PET], etc.) will continue on the specified schedule relative to the subject's first dose regardless of any treatment delay incurred.

Study treatment (BMS-986205, nivolumab and ipilimumab [where applicable]) administration should be delayed for the following:

- Grade 2 non-skin, drug-related AE, with the exception of fatigue, nausea, vomiting and anemia
- Grade 2 drug-related creatinine, AST, ALT and/or Total Bilirubin abnormalities
- Grade 3 skin, drug-related AE
- Grade 3 drug-related fatigue, nausea, vomiting, and anemia
- Grade 3 drug-related laboratory abnormality, with the following exceptions:
 - Grade 3 lymphopenia or asymptomatic amylase or lipase elevations do not require dose delay
 - Grade ≥ 3 AST, ALT, Total Bilirubin will require dose discontinuation in most cases (see [Section 4.5.6](#) for details)
- Any AE, laboratory abnormality, or intercurrent illness which, in the judgment of the investigator, warrants delaying the dose of study medication

In addition, **only BMS-986205** should be delayed for the following:

- Methemoglobin $\geq 15\%$
- Clinically significant elevations in methemoglobin (generally 10% with a normal hemoglobin level⁵⁵) with any associated Grade 3 AE (hypoxia, dyspnea, confusion, etc) attributable to sustained elevations of methemoglobin and not attributable to another etiology

- QTcF > 500 msec confirmed by at least 1 repeat ECG and at least 60 msec above baseline (See [Appendix 8](#)).

If nivolumab or (and ipilimumab in Part 3) dosing is delayed for reasons other than study drug toxicity (eg, administrative issues, holidays, etc), BMS-986205 dosing should continue uninterrupted.

Participants may continue to receive nivolumab (and ipilimumab in Part 3) during dose delays of BMS-986205 for elevations of methemoglobin and associated events, as well as QTcF prolongations.

For participants with methemoglobin elevations with associated Grade 3 AEs, if contribution of nivolumab (and ipilimumab in Part 3) to the associated AE cannot be ruled out (eg, a participant with dyspnea in whom pneumonitis has not yet been ruled out), nivolumab (and ipilimumab in Part 3) dosing should be delayed as well. See [Section 4.5.7](#) for management of methemoglobinemia.

If BMS-986205 dosing is delayed, dose reduction may be necessary. See [Section 4.5.3](#).

If dosing is resumed after a delay, BMS-986205 may be resumed as soon as the criteria to resume treatment are met (see [Section 4.5.5](#)). Nivolumab (and ipilimumab in Part 3) should be resumed as soon as possible after criteria to resume treatment are met but may be resumed later than BMS-986205 given the differences in each drug's administration.

Participants who require delay of any study treatment should be re-evaluated weekly or more frequently if clinically indicated and resume dosing when criteria to resume are met.

4.5.5 Criteria to Resume Treatment

- Subjects experiencing AEs not meeting criteria for permanent discontinuation as outlined in [Section 4.5.6](#) may resume treatment with study drug under the following criteria:
- Subjects may resume treatment with study drug when the drug-related AE(s) resolve to Grade ≤ 1 or baseline value with the following EXCEPTIONS:
 - Subjects may resume treatment in the presence of Grade 2 fatigue.
 - Subjects who have not experienced a Grade 3 drug-related skin AE may resume treatment in the presence of Grade 2 skin toxicity.
- Grade 2 eye pain or blurred vision not meeting DLT criteria ([Section 4.5.1](#)) must resolve to baseline prior to resuming study drug.
- Drug-related pulmonary toxicity, diarrhea, or colitis must have resolved to baseline before treatment is resumed.
- Subjects with drug-related endocrinopathies adequately controlled with only physiologic hormone replacement may resume treatment.
- If the criteria to resume treatment are met, the subject should restart treatment at the next scheduled time point per protocol.
- The consideration to re-initiate study drug under these exceptions will be made on a case-by-case basis after considering the overall benefit/risk profile and in consultation between the

investigator and the BMS Medical Monitor. Any AE with clinical risk will be assessed on a case-by-case basis with the investigator and the BMS Medical Monitor to determine the risks and benefits of continuing therapy following resolution versus discontinuing therapy permanently.

- If treatment with study drug is delayed > 6 weeks from the last dose of BMS-986205 and /or nivolumab (and ipilimumab, where applicable), the subject must be permanently discontinued from study drug, except as specified in [Section 4.5.3](#).

